8.2. Study Design Considerations

Limited therapies exist to treat thrombocytopenia in WAS/XLT. IV gammaglobulin and corticosteroids, mainstays in ITP, are ineffective in WAS/XLT. Platelet transfusions only last for hours. The two treatments that affect the platelets in a more lasting manner are splenectomy and human stem cell transplantation (HSCT). Splenectomy successfully increases the platelet count in most patients but is associated with an increased risk of overwhelming post splenectomy sepsis (OPSS) due to the primary immune dysfunction seen in WAS/XLT. Human Stem Cell Transplantation (HSCT) is effective but has significant morbidity and mortality. Furthermore it is ideally postponed until after 24 months of age to allow TBI, which is too long to wait for affected infants with severe thrombocytopenia in view of the high risk of ICH. It is clearly necessary to establish improved therapy for thrombocytopenia in these children.

8.2.1. Sample Size Assumptions

Zero responders among 15 subjects would suggest that the true proportion responding (i.e. what would be observed if an inordinate number of subjects were studied) is unlikely to exceed 20%.

8.2.2. Sample Size Sensitivity

Zero responders among 15 subjects would suggest that the true proportion responding (i.e., what would be observed if an inordinate number of subjects were studied) is unlikely to exceed 20%.

8.3. Data Analysis Considerations

Data from all subjects who receive eltrombopag will be summarized. Results will be summarized by visit. All displays should include the number of subjects with available data at that visit.

Study endpoints include bleeding score, platelet count, platelet function, megakaryopoiesis and platelet formation.

8.3.1. Key Elements of Analysis Plan

Complex statistical analyses would not be appropriate for an exploratory study. Study endpoints will be summarized by visit using descriptive statistics (mean, median, standard deviation, range) or frequency counts, (as appropriate).

8.3.1.1. Efficacy Analyses

Primary endpoint will be increasing platelet counts in WAS/XLT patients to above 50,000/ul. The generalizability of the data will depend upon including both WAS and XLT patients but no specific distribution of patients within these 2 groups is pre-specified. The proportion of patients showing this increase will be summarized with 95% confidence intervals. The proportion of patients maintaining this increase will be summarized for time points of interest.

Correlations will be evaluated graphically. In addition, Spearman rank correlation coefficients may be used to evaluate the association of platelet count and bleeding score, at each visit.

Any within-subject analyses may be based on Wilcoxon signed rank tests.

Secondary endpoints will involve reduction of bleeding in treated patients within 12 weeks, and to specifically examine the reduction in bleeding in those with platelet counts > 100,000/ul and also > 50,000/ul.

We anticipate that platelet function will improve as the platelet count increases but not normalize.

Therefore efficacy will depend on platelet counts, immature platelet fraction, platelet function by flow cytometry, and the bleeding score. Since the dose required may vary from patient to patient and may only be changed every 2 weeks, a platelet count > 50,000/ul at any time within the first 12 weeks will be considered a response. Similarly, secondary endpoints involving reduction in bleeding and improvement in platelet function will also be explored within a 4 to 12 week window for assessment.

Toxicity will depend upon adverse events, abnormal liver tests, and other abnormal findings.

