1.2. Rationale

Eltrombopag has been remarkably efficacious in substantially increasing platelet counts in a high percentage of patients with chronic ITP (low platelets). The principal investigator [name] has been involved in various trials using eltrombopag; a recently published article detailing the success of eltrombopag illustrates the utility of this treatment (Gerrits et al, 2015). To greatly reduce or eliminate the risk of intracranial hemorrhage (ICH) in patients with WAS would be highly meaningful, as one of the five patients that we currently follow at our institution with XLT has already had an ICH; this is in keeping with published data. Even a relatively small increase in platelet count could be sufficient to prevent ICH in these patients. The ultimate purpose of providing

thrombopoietic treatment is to prevent serious, primarily intracranial, hemorrhage. Based on its utility in other diseases such as chronic ITP, thrombopoietic therapy appears to be the most promising approach for relieving the thrombocytopenia in WAS patients.

There is a very high rate of very serious bleeding associated with WAS and XLT patients (Ochs and Thrasher, 2006) that far exceeds that seen in almost any other form of childhood thrombocytopenia, including ITP (approximately 0.5%) (Kühne et al, 2003). We are targeting a pediatric population in the hopes of controlling and managing the excessive bleeding that occurs in a high percentage of patients with Wiskott Aldrich Syndrome including X-Linked Thrombocytopenia.

Preliminary analysis of 5 patients enrolled in this study along with 3 additional WAS/XLT patients (Gerrits et al, 2015) show that 5 of 8 WAS/XLT patients (3 XLT and 2 WAS) who were on eltrombopag treatment of at least 1 month (1 adult and 4 children) were platelet responders, as evidenced by achieving at least one platelet count $\geq 50 \times 10^9/L$ and double the baseline count. Six of 8 patients had reduced bleeding symptoms. Four eltrombopag-treated patients had platelet counts $\geq 20 \times 10^9/L$ above baseline counts and 4 patients reached counts $\geq 100 \times 10^9/L$.

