3. INVESTIGATIONAL PLAN

3.1. Study Design

Fifteen patients (approximately 80% children) with WAS/ XLT will be enrolled and undergo baseline screening including not only blood drawing but also history of illness in the past, while ten additional WAS and XLT otherwise ineligible or unwilling patients who will not undergo study treatment and ten control subjects will undergo a one-time blood draw. The pediatric control and non-treatment WAS/XLT subjects will be pediatric patients who are having their blood drawn for reasons not related to an acute illness and will provide a limited amount of additional blood. The pediatric control and non-treatment WAS/XLT subjects will have their blood drawn at Cornell after giving consent. They will not be asked for more than 5-10 ml of blood per year of age up to a maximum of 30 ml total in one draw. Blood drawn will be studied for stem cells and

megakaryocytopoiesis, Immature Platelet Fraction (IPF), and platelet function (see table). These subjects will have their blood drawn for another purpose e.g. pre-op clearance for surgery and therefore it will be a small amount of extra blood posing a minimal risk to the subject. Subsequently, treatment patients will start on 2 mg/kg of eltrombopag and be seen every two weeks in the first month, and monthly for the first year. Although Promacta is commercially available in 25 mg and 50 mg tablets, it is also available for clinical studies in 12.5 mg tablets which will be provided by Novartis for this study. In this study, the starting dose will be based upon weight; patients over 50 kg will start at 50 mg daily unless they are of East Asian origin in which case they will use 25 mg as their initial dose. The dose of eltrombopag will be titrated for each subject based on their platelet response (see table 1). Overall, in this study, doses between 12.5mg every other day and 75mg once daily are anticipated to be required to maintain platelet counts between 50 and 400Gi/L. However, as explained in the provided dosing guidelines, the dose of eltrombopag will be reduced whenever the platelet count exceeds 200Gi/L in order to prevent it from reaching 400Gi/L. The goal is to have a platelet count in a safe hemostatic range, albeit not necessarily a normal platelet count.

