Treatment will be initiated at Cornell. Patients will be seen either at Cornell or by a their local doctor 1-3 months thereafter. A recently developed bleeding score, designed to incorporate the four leading bleeding scores, will be administered on study visits to semi-quantitatively assess bleeding.¹⁴ The Page bleeding score is completed using the information from this questionnaire. The hypothesis is that patients with Wiskott-Aldrich Syndrome will have more bleeding at given platelet counts than will patients with ITP. Furthermore the degree of bleeding will correlate not only with the platelet count but with the degree of platelet dysfunction. Platelet size will be explored also. We anticipate the platelet function and bleeding scores will improve with the institution of Promacta therapy if the

platelet counts increase. Even if some of these changes in bleeding are small, the overall direction will help to clarify the effect of treatment on these scores.

There is no placebo; thus, patients will be compared to themselves descriptively before and after treatment through complete physical examinations, complete blood draws, urinalysis, and platelet studies.

[name] has an appointment at Memorial Sloan Kettering, so a patient initiated at Cornell can be followed with appropriate testing at the MSKCC site. In addition, a patient who comes to the Cornell site to provide consent and initiate treatment may be followed at another site for local Laboratory Testing.

Urinalysis, Admission Panel (including liver tests), CBC with Platelet and Differential, PT/PTT, PFA, Fibrinogen, D-Dimers, Platelet Function Analysis, Immature Platelet Fraction (Platelet Reticulocyte Count), and Single Platelet Flow Cytometry will be assessed.

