4. SUBJECT SELECTION AND WITHDRAWAL CRITERIA

4.1. Number of Subjects:

25 WAS/XLT Patients (10 of whom will have a blood draw only) + 10 Normal Control Patients = 35 Total Patients

4.2. Inclusion Criteria:

In order to be eligible for study entry, subjects must comply with the following:

- Males or females from 3 months to 80 years old
- Signed written informed consent obtained prior to study entry
- Clinical diagnosis of WAS or XLT
- Platelet levels less than $75 \times 10^9/L$
- Adequate renal and hepatic function (creatinine and bilirubin less than or equal to $1.5 \times ULN$, AST and ALT less than or equal to $2.5 \times ULN$)

4.3. Exclusion Criteria:

Any patient is ineligible for study entry if he/she:

- Over the age of 80
- Pregnant or lactating women
- Fertile men who are not practicing or who are unwilling to practice birth control while enrolled in the study or until at least 6 months after treatment

- Aspirin, aspirin-containing compounds, salicylates, non-steroidal anti-inflammatory medications (NSAIDS), clopidogrel or ticlopidine, warfarin or other vitamin K antagonists, unfractionated or low molecular heparin within 7 days of first treatment
- Red blood cell transfusion in the past four weeks
- Elevated ($> 1.5 \times$ ULN) prothrombin time (PT) or partial thromboplastin time (PTT)
- New York Heart Classification III or IV heart disease. Other severe cardiovascular or cardiopulmonary disease, including COPD.
- Known HIV infection, hepatitis B or C infection
- Any infection requiring antibiotic treatment within 3 days
- Other concurrent medical or psychiatric conditions that, in the Investigator's opinion, may be likely to confound study interpretation or prevent completion of study procedures and follow-up examinations.
- Prior malignancy with less than a 5-year disease-free interval, excluding nonmelanoma skin cancers and carcinoma in situ of the cervix

Eligibility criteria for controls:

- a) Within 5 years of the age of the enrolled patient
- b) No overt hematologic diagnosis
- c) Male

4.4. Withdrawal Criteria:

1. Treatment with eltrombopag should be discontinued because of abnormal liver tests if any of the following 4 conditions apply:

- ALT levels ≥ 3 times upper limit of normal (ULN) and bilirubin levels > 1.5 times ($> 35\%$ conjugated bilirubin) ULN,
- (2) ALT levels ≥ 3 times ULN and appearance or worsening of hepatitis symptoms or rash,
- (3) ALT levels remain ≥ 3 times ULN for ≥ 4 weeks, or

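### The bleeding subsets at >50,000/µL and >100,000/µL are set by on-treatment counts, are nested, and are not shown beside patients who stayed at or below 50,000/µL

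*Combined protocol and SAP*

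**What the plan says.** Section 8.3.1.1 (Efficacy Analyses) starts with everyone: "Secondary endpoints will involve reduction of bleeding in treated patients within 12 weeks". The same sentence then adds a plan to "specifically examine the reduction in bleeding in those with platelet counts > 100,000/ul and also > 50,000/ul". It does not say at which visit, or over which window, the count must be met. For the primary endpoint the section states that "a platelet count > 50,000/ul at any time within the first 12 weeks will be considered a response", but it does not say that this rule also defines the bleeding subsets. It adds that bleeding and platelet function will be explored in a window of 4 to 12 weeks.

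The same section plans to look at correlations graphically. It allows, without requiring, Spearman coefficients between count and bleeding score at each visit, and Wilcoxon signed-rank tests within subjects. Section 8.3.1 describes the study as exploratory and its summaries as descriptive.

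On the design, Section 3.1 says: "There is no placebo; thus, patients will be compared to themselves descriptively before and after treatment". It also anticipates that "bleeding scores will improve with the institution of Promacta therapy if the" platelet counts rise. The untreated WAS/XLT patients and the controls give a single blood draw (Sections 3.1 and 5.7). Section 4.2 admits patients with counts below 75 x 10^9/L.

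**The concern.** The expectation in Section 3.1 is conditional: bleeding improves if counts go up. Testing it needs a contrast between patients, or periods, with and without a rise. The subset look gives only one side. If bleeding fell just as much in patients who never passed 50,000/µL, the rows above 50,000/µL and above 100,000/µL would look exactly the same. Natural fluctuation, time on study, or milder disease in those who respond could each produce the fall.

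Three features of the plan add to this:

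- **Nesting.** Every patient above 100,000/µL is also above 50,000/µL. Two favourable rows could be taken for a dose-response pattern when they are largely the same people.
- **Entry limit.** A patient entering between 50 and 75 x 10^9/L can be in the >50,000/µL subset without any rise.
- **Dose adjustment.** The table in Section 10 (item 2) makes significant bleeding a reason to increase the dose. Bleeding can therefore influence later counts, and so subset membership.

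At stake is the reading of a secondary endpoint, not the primary result.

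**Working it through.** **1. The plan's own figure.** No figure in the plan concerns the bleeding subsets. The only design figure is in Sections 8.2.1 and 8.2.2: with 0 of 15 responding, the true rate is unlikely to exceed 20%. The rule of three gives 3/15 = 20.0%, and the exact one-sided 95% limit is 1 - 0.05^(1/15) = 18.1%. The figure is reproduced, and nothing below alters it.

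**2. Are the subsets on-treatment?** Entry requires a count below 75 x 10^9/L, so a count above 100,000/µL can be reached only after entry. The >50,000/µL cut-off matches the on-treatment response definition, although some patients may already exceed it at entry.

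**3. Is another comparator available?** No. There is no placebo, and the untreated patients and controls have one blood draw, so they cannot supply a bleeding change. The only candidates are treated patients who stay at or below 50,000/µL.

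**4. Size of the overlap.** Section 1.2 reports "5 of 8 WAS/XLT patients" as responders (at least 50 x 10^9/L and double the baseline) and 4 reaching at least 100 x 10^9/L. Section 3.1 gives the number treated: "Fifteen patients (approximately 80% children) with WAS/ XLT will be enrolled". Suppose that the 4 are among the 5, that nobody else passed 50, and that the rates carry over:

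- above 50,000/µL: 15 x 5/8 = 9.4
- above 100,000/µL: 15 x 4/8 = 7.5
- between the cut-offs: 15 x 1/8 = 1.9
- at or below 50,000/µL: 15 x 3/8 = 5.6
- shared fraction: 4/5 = 80%
- correlation of the two subset means, with equal and independent patient variances: sqrt(4/5) = 0.89

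Section 1.2 does not say that the 4 are among the 5. Its definition also required doubling, which Section 8.3.1.1 does not. Between 5 and all 8 of those patients could have passed 50. At the other extreme the shared fraction is 4/8 = 50%, the correlation is sqrt(4/8) = 0.71, the middle band holds 15 x 4/8 = 7.5 patients, and nobody stays at or below 50,000/µL. The overlap is thus 50% to 80% on these data. Three of the 8 patients were not enrolled in this study.

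**5. What selection on count can do.** This is an illustrative simulation in which treatment has no effect on bleeding. It assumes four post-baseline visits, independence between visits, an assumed within-visit correlation r between count and bleeding, and cut-offs placed so that 5/8 and 4/8 of patients exceed them at their best visit. Mean bleeding change, in SD units:

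| r | All treated | >50,000, peak-count visit | >100,000, peak-count visit | >50,000, mean of visits | >100,000, mean of visits | <=50,000, mean of visits |
|---|---|---|---|---|---|---|
| 0 | 0.00 | 0.01 | 0.01 | 0.00 | 0.00 | 0.00 |
| -0.3 | 0.00 | -0.43 | -0.48 | -0.06 | -0.08 | +0.11 |
| -0.5 | 0.00 | -0.73 | -0.80 | -0.12 | -0.15 | +0.19 |

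If count and bleeding fluctuate together, the subset shows a reduction although the average over all treated patients is zero. The row at or below 50,000/µL reveals this: at r = -0.3, 0.625 x (-0.064) + 0.375 x 0.108 = 0.00. The apparent reduction is large at the peak-count visit and small when averaged over visits, so the unspecified visit matters. With r = 0 this mechanism produces nothing.

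**The case against.** The strongest reply is that the plan already covers most of this. Bleeding is first to be examined in all treated patients, so a reader who infers that bleeding is examined only in those above a threshold, or that lower-count patients drop out of the bleeding analysis, is mistaken. The graphs and the optional Spearman coefficients use everyone with data. The lack of a comparator is disclosed and limits every before-and-after result here. Cumulative thresholds are an ordinary descriptive display, and no test or claim is attached to them.

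All of that stands, and it keeps the point small. It does not remove it. The Spearman analysis is optional and cross-sectional, so milder disease in patients with higher counts could produce it, and it does not compare change in bleeding. Nothing forbids a row at or below 50,000/µL, but nothing plans one either.

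Two objections also limit the remedy. Bands of best count are still selected on an on-treatment outcome, so they show association only. A within-patient contrast of visits above and below 50,000/µL might be taken as the clean answer. It is not: it leaves out patients who never cross 50,000/µL, and in responders the lower-count visits will tend to come earlier, which confounds it with time on treatment. Paired observations may also be few, since the Schedule of Events footnote has first-year blood draws monthly but clinic visits every 3 months.

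**Conclusion.** The point holds as a limit on interpretation, of minor severity. The two bleeding subsets rest on an on-treatment outcome, overlap by construction, have no stated defining window, and are not set beside patients who stayed at or below 50,000/µL. They cannot show that bleeding improves when counts rise, and the >50,000/µL subset can include patients whose counts did not rise.

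The nesting and the missing row follow from the text. The sizes are illustrative: the overlap rests on carrying 8 early patients over to 15, and the simulated shifts rest on an assumed correlation, number of visits and independence between visits.

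A reader might infer that the efficacy analysis is flawed or that the trial's conclusions are at risk. The documents do not support that: the subset look is an exploratory addition, and no primary endpoint, sample-size statement or error rate depends on it.

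**What to change.** In Section 8.3.1.1:

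1. Keep bleeding change in all treated patients as the first result, as already planned.
2. Replace the two nested subsets with three exclusive bands of best count within the first 12 weeks: <=50,000/µL, >50,000 to 100,000/µL, and >100,000/µL. For each band give the number of patients, the baseline count, and the bleeding change from baseline. State which bleeding score is used, for example the mean over the plan's own 4-to-12-week window and not the score at the peak-count visit.
3. Describe the banded results as association, not treatment effect.
4. Optionally, as a supportive summary using on-treatment visits only, take each patient's mean bleeding score at visits above 50,000/µL minus the mean at visits at or below it, summarised with the Wilcoxon signed-rank test. State that it covers only patients with visits on both sides and is confounded with time on treatment.

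The cost is one extra table column and, if step 4 is used, one derived variable per patient. No new data are needed. The drawback is very small bands: about 2 of 15 patients in the middle band if the early rates in Section 1.2 apply, so individual values may be more useful there than summary statistics.

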2.2. Secondary Objective

- This study aims to explore the functional state of circulating platelets in patients with WAS and to relate it to clinical bleeding. Furthermore to demonstrate whether a thrombopoietic agent, eltrombopag, administered daily will increase platelet production and platelet count, and reduce bleeding in patients with WAS.

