Eltrombopag starting doses for children < 50kg will be scaled by body weight and the starting dose will be approximately 2 mg/kg once daily unless they are of East Asian origin in which case they will use approximately 1 mg/kg as their initial dose. This starting dose is based on the findings of GlaxoSmithKline's PETIT2 study: Eltrombopag for children with chronic immune thrombocytopenia (PETIT2): a randomised, multicentre, placebo-controlled trial.

This dosing schedule is based on those used in GlaxoSmithKline's 'PETIT' study: Eltrombopag in Pediatric patients with Thrombocytopenia from ITP.

For young children unable to swallow a tablet, eltrombopag powder for oral suspension (Eltrombopag PfOS) will be used. Each sachet contains eltrombopag equivalent to 20mg per gm of powder. Please see Appendix 3 for details and dose adjustment guidelines for subjects receiving the suspension formulation. Repeat assessment with the same testing will be performed at week 4. Dose adjustment will be based on the monthly monitoring of the platelet count.

The IPF will be measured at each visit with the CBC. Platelet count data will be collected throughout the study and used as part of the assessment of efficacy. Platelet count data will be collected as part of the CBC monthly during the first year of administration of study drug and at any dose change (eltrombopag or concomitant medication). If a subject continues on a stable dose during any stage of the study for greater than 4 weeks, a CBC (including platelet count) with differential will be performed no less frequently than every 4 weeks. Further information regarding reduction in use of concomitant medications for thrombocytopenia, use of rescue therapy, incidence and severity of bleeding and other symptoms associated with thrombocytopenia and infections will also be collected and summarized.

Platelet function will be assessed by whole blood flow cytometry as described by and in collaboration with [name] (see appendix for attached abstracts).

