8. DATA ANALYSIS AND STATISTICAL CONSIDERATIONS

8.1. Hypotheses

The primary objective is to describe the pathophysiology of thrombocytopenia and bleeding in patients with Wiskott-Aldrich Syndrome (WAS) and determine the response to thrombopoietic agents *in vitro* and *in vivo*.

SPECIFIC AIMS:

1. To explore stem cell function in patients with WAS
2. To evaluate the functional state of circulating platelets in patients with WAS and relate it to clinical bleeding
3. To demonstrate whether a thrombopoietic agent, eltrombopag, administered daily will enhance stem cell function, increase platelet production and platelet count, and reduce bleeding in patients with WAS

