

SCHEDULE OF EVENTS
“Pathobiology of Thrombocytopenia and Bleeding in Patients with Wiskott-Aldrich Syndrome.” Protocol #: 0801009600

	Screening	Day 1/Baseline	Week 2	Week 4	Months ⁴ 2 – 12	Months ⁵ 14 - 24	Months ⁶ 27 - 72
Evaluation and Management							
Informed Consent	x						
Bleeding Score ¹	x	x	x	x	x	x	x
Standard of Care							
Physical Examination	x	x	x	x	x	x	x
Urinalysis	x						
Admission Panel (Includes liver tests such as ALT, AST, bilirubin)	x	x	x	x	x	x	x
CBC with Platelet and Diff	x	x	x	x	x	x	x
Diagnostic Tests for Platelet Function							
PT/PTT	x						
D-Dimers	x						
Fibrinogen	x						
PFA ²					x		
Immature Platelet Fraction (Platelet Reticulocyte Count) ³	x	x	x	x	x	x	x
Single Platelet Flow Cytometry ⁷	x			x	x ⁸		

1. The Page bleeding score will be administered at each visit in order to semi-quantitatively assess bleeding
2. PFA (Platelet function Analysis) will be assessed once for WAS/XLT patients and control patients at month 2, provided platelet count is >50 k
3. IPF will be obtained with each Cornell in-clinic CBC where possible
4. Subjects will have their blood drawn monthly and be seen every 3 months during the first year
5. Subjects will have their blood drawn every 2 months and be seen every 4 months in the second year
6. Subjects will have their blood drawn every 3 months and be seen every 6 months in the 3rd – 6th years
7. Single Platelet Flow Cytometry tests will be performed by [name] at screening, once between months 1-3, and once after 1-2 years on study.

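### The immature platelet fraction is the only scheduled repeated marker of platelet production apart from the count, and it can stay flat or fall when production truly rises; add the absolute immature platelet count

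*Combined protocol and SAP*

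**What the plan says.** Section 8.1, Aim 3, asks whether daily eltrombopag will, among other things, "increase platelet production and platelet count, and reduce bleeding in patients with WAS". The secondary objective in Section 2.2 uses the same clause. Production and count are thus separate targets.

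Section 8.3.1.1 then states: "Therefore efficacy will depend on platelet counts, immature platelet fraction, platelet function by flow cytometry, and the bleeding score". It gives no favourable direction for IPF, does not say which aim IPF serves, and does not say how IPF and the count are to be read together. The response itself is defined on the platelet count alone (above 50,000/ul at some point in the first 12 weeks). Section 8.3.1 calls for descriptive summaries by visit, and 8.3.1.1 allows Wilcoxon signed rank tests within subjects.

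Other production-related items are named. Section 8.3 says: "Study endpoints include bleeding score, platelet count, platelet function, megakaryopoiesis and platelet formation". Section 3.1 lists stem cells and megakaryocytopoiesis among the blood studies. Neither the table in Section 5.7 nor the Schedule of Events has a row for an assay of these.

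On sampling, Section 3.1 says: "The IPF will be measured at each visit with the CBC". Section 5.7 puts IPF and the CBC in one 2 mL row. Footnote 3 of the Schedule is narrower: "IPF will be obtained with each Cornell in-clinic CBC where possible". The Schedule row is labelled "Immature Platelet Fraction (Platelet Reticulocyte Count)", which puts the word count in brackets after a fraction. No section defines an absolute immature platelet count.

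**The concern.** IPF is a ratio: immature platelets over all platelets. A drug that makes the marrow release more platelets raises the numerator and, once the count has settled, the denominator too. If survival is unchanged, the ratio ends where it began. If survival also lengthens, the ratio falls. A production increase therefore has no fixed sign on this scale, and the plan states no sign.

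What is at stake is mechanism. A platelet count that rises on treatment may mean that more platelets are made, that they last longer, or both. The primary objective is about pathophysiology and Aim 3 names production, so the distinction is part of what the study sets out to learn. A by-visit table with IPF flat or falling invites the reading that production did not change, and that reading could be wrong.

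**Working it through.** **Plan's own figure.** The plan gives no figure for IPF. Its one design figure (Sections 8.2.1 and 8.2.2: no responders in 15 makes a true rate above 20% unlikely) reproduces by the rule of three, 3/15 = 20%. The exact one-sided 95% limit is 1 − 0.05^(1/15) = 18.1%. This point does not depend on it.

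**Inputs.** From the documents: 15 treated patients (Section 3.1), untreated counts often below 10,000–30,000/ul (Section 1.1), and the optional Wilcoxon test (8.3.1.1). Not in the documents, so assumed: baseline IPF, the size of the production change, and assay noise.

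**Steady-state relations.**
- Platelet count = production × lifespan.
- Immature count = production × immature period.
- IPF = immature count / platelet count = immature period / lifespan. Production cancels, whatever the baseline IPF.

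**Numbers**, from an assumed 20,000/ul at IPF 5%, so 20,000 × 0.05 = 1,000 immature/ul, with the immature period held constant:

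| Production | Lifespan | Count /ul | Immature /ul | IPF |
|---|---|---|---|---|
| ×3 | ×1 | 60,000 | 3,000 | 5.0% |
| ×2 | ×1.5 | 60,000 | 2,000 | 3.3% |
| ×1 | ×3 | 60,000 | 1,000 | 1.67% |
| ×2 | ×0.75 | 30,000 | 2,000 | 6.7% |

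The first three rows share one count, so the count alone cannot tell them apart. IPF read alone shows no change in the first row and a fall in the second, although production rose in both. The absolute immature count follows production in every row.

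**Within-subject test.** A simulation used 15 pairs and 3,000 runs per setting. Production doubled in the median patient (log SD 0.3) with lifespan unchanged. Baseline counts were 10,000–30,000/ul, baseline IPF 2–20%, and count noise 0.2 (log SD). Share of runs with p < 0.05:

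| IPF noise (log SD) | IPF | Absolute immature count | Platelet count |
|---|---|---|---|
| 0.2 | 4.7% | 99.6% | 100% |
| 0.3 | 5.8% | 96.6% | 100% |
| 0.5 | 5.2% | 80.2% | 100% |

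IPF rejects at about the false-positive rate. The count detects the change every time here because lifespan was held fixed; it does not show that production was the cause.

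**Can the product be rebuilt from planned summaries?** Not from group summaries. Take two assumed patients, 10,000/ul at 20% and 30,000/ul at 5%. Their immature counts are 2,000 and 1,500, mean 1,750. Multiplying the means gives 20,000 × 12.5% = 2,500. The product must be formed per patient.

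**Limit of the alternative.** Because immature count = production × immature period, a change in the immature period also moves it. With production and lifespan unchanged and the immature period 1.5 times as long, it would go from 1,000 to 1,500/ul and IPF from 5% to 7.5%.

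**The case against.** A reader might infer that the plan judges production by IPF alone. No section says so. Section 8.3.1.1 lists IPF among four efficacy measures without tying it to the production clause, and Sections 8.3 and 3.1 also name megakaryopoiesis and platelet formation. Section 3.1 further asks for the same testing to be repeated at week 4, which could be read to include megakaryocytopoiesis. This stands as a limit on the wording. It does not remove the point, because those items have no scheduled assay, and in the Schedule only IPF is left to separate production from count.

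A reader might also infer that a real treatment benefit would be reported as no effect. The documents do not support that. The response rests on the platelet count, the count is summarised by visit, and no threshold or stopping rule uses IPF. A patient going from 20,000 to 60,000/ul is a responder whatever IPF does.

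Other fair objections are these:
- The study is exploratory, and the product can be calculated later from patient-level data. True, but a descriptive IPF table carries the same ambiguity, and a measure and direction chosen afterwards are weaker than ones stated in advance.
- The bracketed label in the Schedule may mean that a count is intended. The text supports only that the scale is unclear, which is itself worth settling.
- The absolute count is not a pure production measure, and steady state may not hold while doses can change every 2 weeks (8.3.1.1). Both limits stand and must be stated with the measure.
- Availability is limited. Footnote 3 restricts IPF to certain Cornell draws, footnote 4 has monthly draws but visits every 3 months in year 1, and Section 3.1 allows local laboratory testing. This also stands.

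**Conclusion.** The point holds for the production clause of Aim 3 and the related pathophysiology objective, and no further. As planned, IPF may be flat, lower or higher when production rises, and the plan gives no rule for reading it. In the assumed example a threefold production increase changes IPF by 0% and the absolute immature count by +200%. The primary platelet-count endpoint, the overall efficacy conclusion and the sample-size statement are unaffected.

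That production cancels from IPF follows from the steady-state relations and holds for any baseline IPF. A flat IPF also needs unchanged lifespan and immature period; away from steady state, or if lifespan shortens, IPF can rise. The sizes shown rest on assumed IPF values, fold changes and noise. The absolute immature count is the better production measure on condition that the immature period stays roughly constant and dosing is near steady. The correction should be made before the data are analysed, as a should-fix rather than a threat to the trial.

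**What to change.** In Section 8.3.1.1:
- Define the per-patient absolute immature platelet count as IPF% × platelet count from the same sample, and name it as the measure of platelet production. State that an increase from pre-dose is favourable, and say which pre-dose value is used (the Schedule has IPF at both screening and Day 1).
- Report IPF% and platelet count beside it at each visit.
- State that reading it as production assumes a roughly constant immature period and near-steady dosing.
- Treat the joint reading as supportive only: absolute count up with IPF% flat suggests more production; absolute count flat with IPF% down suggests longer survival.
- Report the number of patients with paired IPF and count values at each visit.

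In the Schedule of Events, make clear whether the IPF row is a fraction, a count or both.

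The cost is one derived variable and a few sentences, with no added blood. The small downside is that the variable will be missing wherever IPF was not obtained, so some visits may have few paired values.
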